2. PURPOSE OF THE RESEARCH

The aim of the present research is to evaluate the efficacy of a mouthwash formulation for a total treatment of 14 days for the treatment of oral ulcers of traumatic or aphthous nature.

The study groups are as follows:

- Group I (Test): Curasept Canker Sores Rapid Mouthwash: Dicaprylyl Ether, Coco-Caprylate/Caprate, Hydrolyzed RNA/DNA, Hyaluronic Acid, Cetyl Palmitate, Beta-Glucan.

Versus

- Group II (Control): Placebo mouthwash

Null hypothesis (H0): There is no difference at 14 days in the reduction of the mean pain sensation and ulcer area score, thermography [16,17] and Ulcer Severity Score (USS) [18] in the two groups, against the alternative hypothesis of a difference between them.

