6.1 Evaluation of the primary objectives

- Pain intensity. It will be measured using the VAS consisting of a 10 cm line [13], where 0 indicates no pain and 10 indicates severe pain.
- Size of each ulcer. A sheet of transparent plastic will be applied directly to the ulcer and using a permanent waterproof marker the circumference of the ulcer has been traced and then placed on a graph paper counting them units of mm² included within the drawn area. Treatment will begin on the same day with strict infection control measures.

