7.3 Statistical analysis

Descriptive statistics will be provided in summary tables by group based on the type of outcome measure summarized.

General descriptive statistics for continuous outcome measures will include n (number of observed values), mean with its 95% CI, standard deviation, median, minimum and maximum values. For categorical variables, the number and percentage of subjects with a specific level of the variable will be presented.

This primary efficacy analysis will be performed on ITT, using the null hypothesis of no between-group difference in overall VAS change from baseline between both groups:

$$H_0: \mu_{\text{AfteRapidDNA}} = \mu_{\text{Placebo}}$$

$$H_1: \mu_{\text{AfteRapidDNA}} \neq \mu_{\text{Placebo}}$$

Where μ is the mean change from baseline on Day 7 within the given product.

This hypothesis will be tested with an Analysis of Variance (ANOVA) with baseline values of VAS as a covariate. The groups will be compared to the bilateral significance level of 5%.

The assumption of normality will be verified by means of QQ graphs and by plotting the studentized residuals with respect to the expected values of the variable. If there are strong indications of non-normality of the data, the Wilcoxon Rank-Sum Test will be used to test the hypothesis of no median difference between buccacollutorio and placebo at Day 7 in a nonparametric manner. Summaries for each treatment group will include sample size, mean, median, standard deviation, minimum, maximum, Wilcoxon Rank-Sum test p-value, Hodges-Lehman point estimates of median treatment difference, and its 95% confidence interval.

From the Day 7 endpoint ANOVA model, a least squares estimate (LSMEANS) of the group effect and group difference (both with 95% confidence intervals) will be displayed along with the p-value of the difference between the groups.

Analysis will also be performed for the PP Analysis Set to test the robustness of the results.

For secondary quantitative efficacy variables, cross-treatment group comparison of change from baseline will be done by the same ANOVA model used in the primary efficacy analysis. Categorical derived variables (complications/adverse events) will be compared via a chi-square test or Fisher's exact test, as appropriate (chi-square test will be used if all groups have sufficient observations,

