otherwise Fisher's exact test will be used). All statistical comparisons will be conducted at the significance level 0.05. SAS version 9.4 will be used for scanning.

8 Data management

An electronic CRF (eCRF) will be completed by the Investigator and/or his/her delegate.

All patients who sign the informed consent will be archived. A minimum set of information is required for patients who are screened but not randomized: date of signed informed consent, demographics, assessment of inclusion/exclusion criteria where applicable, primary reason for non-continuation, adverse events, and any concomitant medications.

Front-end change checks will be performed at the time of data collection, and back-end change checks will be used by the Data Manager to check for discrepancies and ensure data consistency and completeness.

Administrative practices and data management

Medical record forms (CRFs) must be completed at the time of data collection. The complete CRF memory device containing the digitized clinical images should be attached to each patient's study file.

All data required for this study will be collected using paper-based CRFs. CRFs will be kept in a secure, locked location that will only be accessed by the Principal Investigator and the data collector. The data will also be accessible to the sponsor for monitoring and evaluation purposes at its discretion. After completion of the 1-week follow-up, copies of all CRFs will be sent to the investigator who will check the data and store them in a protected computer with a password known only to him. The data will be processed by an expert statistician. The patient's identity will be protected and known only to the study participants listed in this protocol.

Case Report Forms (CRFs)

- Patient informed consent form
- CRF Patient Eligibility
- CRF Rating
- Complications, protocol deviation and CRF drop-out

Changes and violations of the Protocol

Changes to this protocol may be necessary, and protocol violations are likely to occur. Any protocol violation should be reported in the "Complications, Protocol Deviation, and CRF Dropout" section. If you experience any problems, contact your studio monitor immediately.

Data Ownership

The data belongs to the sponsor.

Essential bibliography

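### The plan has four, two or one key outcomes depending on the section, and no testing order: Day 7 VAS alone keeps 5% error, but a claim on any listed outcome carries about 7–19%

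*Combined protocol and SAP*

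**What the plan says.** Three parts of the document describe the trial's question differently.

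- **Section 2 (Purpose of the research)** has a single null over four outcomes, "mean pain sensation and ulcer area score, thermography [16,17] and Ulcer Severity Score (USS) [18] in the two groups". Its time point is Day 14: "There is no difference at 14 days in the reduction". The alternative is simply that the groups differ.
- **Sections 4.4 and 6.1** list two primary outcomes, VAS pain and ulcer size ("Size of each ulcer. A sheet of transparent plastic will be applied directly to the ulcer"), and do not rank them. Sections 4.4 and 6.2 make thermography and USS secondary. All four are measured at Day 7 and Day 14.
- **Section 7.3** defines one primary efficacy analysis in the ITT population, "using the null hypothesis of no between-group difference in overall VAS change from baseline between both groups", where the parameter "is the mean change from baseline on Day 7 within the given product". The test is two-sided at 5%. Secondary quantitative variables use the same model, with no visit named. Ulcer size appears neither in the primary hypothesis nor by name among the secondary variables.

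Section 7.3 closes with "All statistical comparisons will be conducted at the significance level 0.05". Nowhere is there an order of testing, a multiplicity adjustment, a rule for when the trial has succeeded, or a statement that some outcomes are descriptive only.

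**The concern.** Section 2 does not say that all four outcomes must differ, so a difference on one of them can be read as rejecting its null. The Section 7.3 primary test does not close this gap, because it is at Day 7 and the Section 2 null is at Day 14. Ulcer size carries the primary label but has no place in the hypothesis. Nothing makes a claim on ulcer area, USS or thermography depend on VAS having succeeded. If VAS shows nothing at Day 7, the plan as written does not stop a single p-value below 0.05 on another outcome from being reported as efficacy. At stake is how often a mouthwash with no effect would be reported as effective.

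**Working it through.** **Inputs.** From Section 7.3: 0.05 per comparison, two-sided. From Section 2: four outcomes at one visit. From Sections 4.4 and 6.1: two primary outcomes. The documents give no correlation between outcomes, so it is assumed and varied from 0 to 0.9. The per-protocol analysis (a robustness check) and the adverse-event comparisons are not counted as efficacy claims.

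**1. The plan's own figure.** With one test, the error is 1 − 0.95 = 5.0%. The Day 7 VAS test keeps its stated level.

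**2. Independent tests.** The chance of at least one p < 0.05 under no effect is 1 − 0.95^k.

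- k = 2: 1 − 0.9025 = 9.75%
- k = 4: 1 − 0.8145 = 18.5%

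**3. Correlated tests.** Equicorrelated standard normal statistics were simulated (1,000,000 draws per setting), counting draws in which any |z| exceeded 1.96.

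| Assumed correlation | 2 listed primaries | 4 outcomes, one visit |
|---|---|---|
| 0 (exact) | 9.75% | 18.5% |
| 0.5 | 9.0% | 15.6% |
| 0.7 | 8.4% | 13.1% |
| 0.9 | 7.0% | 9.4% |

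Some correlation is to be expected. The USS in Section 6.2 includes patient-perceived pain and lesion size, so it overlaps both VAS and ulcer area.

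**4. Both visits, for comparison only.** Testing four outcomes at two visits (k = 8) gives 1 − 0.95^8 = 33.7% if independent, 25.0% at correlation 0.5, 19.1% at 0.7 and 11.9% at 0.9. No section prescribes these eight tests.

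**5. What a Holm step would cost VAS.** Holm's first step uses 0.025 (critical value 2.241 instead of 1.960). The power of VAS under Holm lies between its power at 0.025 and at 0.05.

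- If the VAS test had the 80% power stated in Section 7.1, power at 0.025 would be Φ(0.842 + 1.960 − 2.241) = Φ(0.561), about 71%.
- Section 7.1 prints a difference of 0.820, SD 1.80 and 29 per group, without naming the outcome. If these refer to VAS, the standardised shift is 0.820 / (1.80 × √(2/29)) = 1.735. Power is then Φ(1.735 − 1.960), about 41%, at 0.05 and Φ(1.735 − 2.241), about 31%, at 0.025 (normal approximation).

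The gap between 41% and the stated 80% is a separate matter and does not affect the error rates above.

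**The case against.** The strongest reply is that Section 7.3 governs the analysis and is clear: one primary hypothesis, one outcome, one visit, two-sided 5%. Other efficacy variables are called secondary and the per-protocol set is for robustness. On that reading the primary claim has 5% error. This stands, and it sets the lower end of the range. It does not dispose of the point, because the Section 7.3 test does not address the Section 2 null, leaves the second listed primary unplaced, and makes no other claim conditional on its result.

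A reader might go further and infer that the plan promises an overall 5% and delivers up to about 34%. The documents do not support this, for three reasons.

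- They never state a family-wise rate. The 5% belongs to the primary test, and the 0.05 applies to each comparison.
- The Section 2 null is at Day 14 only, so it covers four comparisons, not eight. Scheduling measurements at both visits is not a plan to test at both.
- The 33.7% also needs eight independent tests. That is implausible with overlapping outcomes and with repeat visits of the same patients sharing a baseline.

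Nor is 13% a floor for four outcomes: at correlation 0.9 the figure is 9.4%.

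**Conclusion.** The point holds in a limited form. The document gives four, two or one key outcomes, and Day 14 or Day 7, depending on the section, with every comparison at an unadjusted 0.05 and no rule linking them. The false-positive risk therefore depends on the reading:

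- 5% if Day 7 VAS is the only claim;
- about 7–10% if either listed primary may be claimed;
- about 9–19% if any of the four outcomes at one visit may be claimed.

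The last two ranges rest on assumed equal correlations from 0.9 down to 0, and on the premise that one significant outcome would be presented as efficacy, which the plan permits but does not state. Figures above 19% apply only if both visits are tested, which is not specified.

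**What to change.** Before any unblinded data are seen:

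1. Reconcile Section 2 (Day 14) with Section 7.3 (Day 7) and name one confirmatory visit. Unless this is done first, a sequence that starts with Day 7 VAS leaves the 14-day hypothesis with no confirmatory test.
2. Replace the joint null in Section 2 with one null per outcome.
3. State one confirmatory sequence in Section 7.3 at the chosen visit: VAS first at two-sided 5%, then ulcer area only if VAS succeeds. Alternatively, use Holm across VAS and ulcer area, since both are listed as primary. USS and then thermography follow in fixed order, only if the preceding tests have all succeeded.
4. Report all other comparisons, including the other visit, as estimates with 95% CIs and no efficacy claim.

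The change is to wording, but it has a price. The fixed order keeps VAS at its full 5% but ranks ulcer area below it although both are listed as primary. Ulcer area could then be claimed only when VAS succeeds: 80% of the time at the stated power, about 41% on the printed inputs if they refer to VAS. Holm avoids that ranking, and VAS then gives up at most about 9 percentage points of power (80% to 71%), or about 10 on the printed inputs (41% to 31%). Under either scheme, isolated secondary p-values below 0.05 can no longer be claimed as efficacy.
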